### **9.5 Study Size**

In phase III studies investigating the interferon-free ABBVIE REGIMEN  $\pm$  RBV, SVR12 rates of at least 90% were observed, even in difficult-to-treat CHC patients (e.g. cirrhotic G1a treatment experienced patients). To describe in routine clinical practice the effectiveness of the ABBVIE REGIMEN  $\pm$  RBV in patients with CHC, a precise estimate of the SVR12 rates in the core population of this study should be achieved (see Section **Error! Reference source not found.** for the definition of the core population).

As obvious from **Error! Reference source not found.**, if the SVR12 rate is at least 90%, then with 417 evaluable patients the width of the 95% confidence interval (CI) will not be wider than 6%. If the SVR12 rate is at least 95%, then 238 patients are sufficient for a width of 6%, and the width of the 95%CI will be  $\leq$  5% if at least 334 evaluable patients can be included. Taken into consideration that about 5% of the patients enrolled might be not evaluable in the core population 440 patients should be enrolled during the planned inclusion period of 24 months.

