#### 9.7.3.3 Statistical Methods for Analysis of Effectiveness Variables

The simple percentage of patients achieving SVR12 will be calculated and an exact two-sided 95% confidence interval (CI) of the percentage will be computed based on the Clopper-Pearson method.

Corresponding methods will be used for other response rates (EoT response rate, relapse rate, viral breakthrough). The relapse rates will be estimated in patients of the CP analysis groups with EoT response and sufficient HCV RNA measurements post-treatment. Viral breakthrough rates will be estimated in all patients of the CP analysis groups, who have at least one undetectable HCV RNA measurement on-treatment and at least one on-treatment or EoT measurement thereafter.

Univariate and multiple logistic regression (MLR) methods will be used to investigate the impact of the following explanatory covariates on SVR12:

- Key demographic information
- Mode of CHC infection
- HCV RNA level at baseline
- Most recent stage of liver fibrosis
- HCV genotype and subtype (if available)
- Type of treating institute
- Liver and/or CHC related co-morbidities
- Key clinical chemistry and hematology laboratory variables at baseline
- In treatment experienced patients only:
  - Most recent prior treatment for CHC
  - Outcome of most recent prior CHC treatment

Further details and additional covariates will be specified in the SAP.

These analyses will be of exploratory nature, data driven, and will be repeatedly performed for various CP Analysis Groups, since not each covariate might be predictive in each patient group. Furthermore, the fact that treatment regimens will differ in the various patient groups has to be taken into account, when selecting the patient groups for each MLR analysis. Backward selection procedures will be applied to generate the final MLR models which consider only covariates in the selection procedure with a p-value

---

Confidential Information

No use or disclose outside AbbVie is permitted without prior written authorization from AbbVie

<0.25 in the corresponding univariate logistic regression analysis. A p-value <0.05 will be used for the covariates to stay in the model in a backward elimination step. Logistic regression methods will also be used to investigate the impact of treatment adherence on SVR12.

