3.2 Sample Size Calculation

In phase III studies investigating the interferon-free ABBVIE REGIMEN \pm RBV, SVR12 rates of at least 90% were observed, even in difficult-to-treat CHC patients (e.g. cirrhotic G1a treatment experienced patients). To describe in routine clinical practice the effectiveness of the ABBVIE REGIMEN \pm RBV in patients with CHC, a precise estimate of the SVR12 rates in the core population of this study should be achieved (see Section 4.2.1 for the definition of the core population).

As obvious from Table 1, if the SVR12 rate is at least 90%, then with 417 evaluable patients the width of the 95% confidence interval (CI) will not be wider than 6%. If the SVR12 rate is at least 95%, then 238 patients are sufficient for a width of 6%, and the width of the 95%CI will be $\leq 5\%$ if at least 334 evaluable patients can be included. Taken into consideration that about 5% of the

patients enrolled might be not evaluable in the core population 440 patients should be enrolled during the planned inclusion period of 24 months.

Table 1 Width of 95% Confidence Interval for SVR12

Number of patients	SVR12 rates	95% Confidence Interval*			Width
		Lower Limit	Upper Limit	Width	
417	90%	86.71	92.71	6.00%	
238	95%	91.41	97.40	5.99%	
334	95%	92.08	97.08	5.00%	

* exact two-sided 95% confidence interval according Clopper-Pearson

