Virological response rates and non-response categories will be displayed for patients who completed treatment with AbbVie regimen, as well.

SVR12 (Exploratory Analyses)

Univariate and multiple logistic regression (MLR) methods will be used to investigate the impact of various explanatory covariates (patient and disease characteristics) at baseline on SVR12.

These analyses will be of exploratory nature, data driven, and will be performed for CP population. Univariate logistic regression will be performed first and then backward selection procedures will be applied to generate the final MLR model. A p-value <0.05 will be used for the covariates to stay in the model in a backward elimination step. If the percentage of patients with available data for a variable is lower than 80% of the patient group analyzed, then this variable will not be considered in the MLR analysis.

The variables to be considered are as follows:

- Key demographic information
 - Age (continuous)
 - Gender (Female [reference], Male)
 - Race/ethnic origin (White/Caucasian [reference], Black, Asian/Oriental, Other [all other races]); at least two categories with at least 10% of the patients each have to exists, so that this variable will be considered
 - Weight (continuous)
 - BMI (continuous)
 - IL28B, rs12979860 (CC [reference], CT or TT); patients with unknown genotype are excluded from the respective analyses.
- CHC disease characteristics
 - Years since diagnosis (continuous)
 - Mode of CHC infection (Drug use [reference], Other [all other answers excluding unknown], unknown);
 - Most recent stage of liver fibrosis (No cirrhosis/Transition to cirrhosis [reference], Cirrhosis; for definition see 4.2.6.2);
- HCV RNA level at baseline (\log_{10} IU/mL)
- HCV genotype(G1a*, G1b, G4; for definition see section 4.2.6.2)
- Type of treating institute (Private Practice / Private Hospital, Academic / University Hospital, General Hospital, Other)
- Co-infections (every patient not reporting the respective co-infection is considered as not having the respective co-infection)
 - HIV(No [reference], Yes)
 - HBV(No [reference], Yes)
- Liver and/or CHC related co-morbidities (every patient not reporting the respective co-morbidity is considered as not having the respective co-morbidity)
 - Liver transplantation (No [reference], Yes)
 - Steatosis (non-alcoholic) (No [reference], Yes)
 - Decompensated liver disease (No [reference], Yes)

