- Other co-morbidities (every patient not reporting the respective co-morbidity is considered as not having the respective co-morbidity)
 - Depression (No [reference], Yes)

- Diabetes mellitus (No [reference], Type 1/Type 2)
 - Hypertension (No [reference], Yes)
 - Immunologically mediated disease (No [reference], Yes)
 - Hypothyroidism (No [reference], Yes)
 - Alcohol use (None [reference], Yes –occasional, Yes –regular, Exdrinker)
 - Key clinical chemistry and hematology laboratory variables at baseline
 - ALT ratio (continuous, see 4.2.6.5)
 - AST ratio (continuous, see 4.2.6.5)
 - Platelets [$10^9/L$] (continuous)
 - Prior treatment status (HCV treatment naïve [reference], HCV treatment experienced)

Additionally, an interaction term for cirrhosis status and genotype will be considered. If the most recent stage of liver fibrosis status (No cirrhosis/Transition to cirrhosis vs Cirrhosis), the genotype (G4, G1b vs G1a) or the interaction of both remains in the final model, then additional MLR might be considered for the subgroups concerned, taking into account the treatment regimen (e.g. in cirrhotic G1 patients: RBV vs no RBV and 12 wks vs 24 weeks).

The categories pre-specified above could be modified in the analyses if this is supported by the data (e.g. categories could be combined, if their impact on SVR12 is similar). Furthermore, continuous variables can be replaced by categorical variables.

Adherence

Adherence will be displayed for the CP by genotype and cirrhosis status and for the SP by treatment regimen and cirrhosis status. Summary statistics (n, mean, median, standard deviation [SD], and range) will be generated for continuous variable. Numbers and percentages of patients will be presented for categorical variables.

- Adherence to Abbvie regimen (% of target dose [adherence=cumulated number of pills taken /(initial prescribed number of pills x planned duration)])
 - >105%
 - >95%--<=105%
 - >80%--<=95%
 - >50%--<=80%
 - <=50%
- Adherence to ribavirin (% of target dose [adherence=cumulated dose taken /(initial prescribed dose x planned duration)])

- >105%
 - >95%-<=105%
 - >80%-<=95%
 - >50%-<=80%
 - <=50%
- Percentage of actual treatment duration in relation to the target duration of ABBVIE regimen taken
- Deviating duration of ABBVIE regimen
 - Early discontinuation (actual duration is shortened for more than 7 days)
 - Not deviated
 - Exceedance (actual duration is prolonged for more than 7 days)

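### The SVR12 predictor model can start from up to 37 parameters on about 21–42 expected non-responders, with the protocol's p<0.25 screen missing from the SAP and no rule for separation or sparse covariates

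*SAP*

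**What the plan says.** SAP 4.2.7.2.1 (exploratory SVR12 analyses) fits logistic models in the core population: "Univariate logistic regression will be performed first and then backward selection procedures will be applied to generate the final MLR model". A covariate stays if p<0.05. The list holds 27 covariates, and then: "Additionally, an interaction term for cirrhosis status and genotype will be considered".

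Three provisions limit the list. A variable available in fewer than 80% of patients is left out of the multiple model. Race enters only if at least two categories each hold 10% of patients. Categories may be merged after looking at the data. The adherence models force adherence in on top of the same covariates, and the ribavirin version uses only patients taking ribavirin.

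Protocol 9.7.3.3 has a further step that the SAP text lacks: "Backward selection procedures will be applied to generate the final MLR models which consider only covariates in the selection procedure with a p-value" below 0.25 in the univariate fit. The protocol abstract says the same.

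SAP 3.2 gives the planning size: "if the SVR12 rate is at least 90%, then with 417 evaluable patients" the interval is at most 6% wide; the other planning rate is 95%. SAP section 6 names SAS 9.4. Neither document names an estimator, a test, a penalised or exact method, or a rule for separation.

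**The concern.** In logistic regression the information is set by the rarer outcome, here non-response. With about one non-responder per candidate parameter or fewer, two things go wrong under ordinary maximum likelihood. Some combination of covariates may separate responders from non-responders, so that estimates diverge and Wald p-values lose their meaning. Finite estimates are also pushed away from 1. If elimination starts from the full list, the first decisions on what to drop are made in the model where both problems are worst.

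At stake are secondary objectives 2 (predictors of response) and 4 (influence of adherence). The SAP introduction hopes that predictors found here could help to optimise treatment, so exaggerated odds ratios may be taken up in practice.

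**Working it through.** **1. Planning figures (SAP Table 1).** Clopper-Pearson limits with x = n·p: lower = Beta quantile(0.025; x, n−x+1), upper = Beta quantile(0.975; x+1, n−x).
- n=417, 90%: 86.71–92.71, width 6.00 (stated 6.00).
- n=238, 95%: 91.41–97.40, width 5.99 (stated 5.99).
- n=334, 95%: 92.08–97.08, width 4.99 (stated 5.00).
- Enrolment: 417/0.95 = 439, against 440 in Protocol 9.5 ("about 5% of the patients enrolled might be not evaluable in the core population 440 patients should be enrolled").

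The planning figures reproduce.

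**2. Parameters, from the SAP list.**
- One each (22): age, gender, weight, BMI, IL28B, years since diagnosis, fibrosis stage, HCV RNA, HIV, HBV, liver transplantation, steatosis, decompensation, depression, diabetes, hypertension, immunologically mediated disease, hypothyroidism, ALT ratio, AST ratio, platelets, prior treatment.
- Two each (4): mode of infection, genotype.
- Three each (9): race, type of institute, alcohol.
- Interaction: 2.

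Total 22+4+9+2 = 37. Without race 34; without race and IL28B 33. Adherence in three categories adds 2.

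**3. Non-responders per parameter.** 417×0.05 = 20.9 and 417×0.10 = 41.7.
- 37 parameters: 20.9/37 = 0.56; 41.7/37 = 1.13.
- 33 parameters: 20.9/33 = 0.63; 41.7/33 = 1.26.

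SAP 4.2.3 counts missing SVR12 as failure, which can raise the count. At an assumed 15% failure rate: 417×0.15 = 62.6, and 62.6/37 = 1.7.

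**4. Empty cells.** A yes/no covariate present in k patients has no non-responder with probability (1−f)^k. For k=12: 0.95^12 = 0.54 and 0.90^12 = 0.28. For k=42 (10% of 417): 0.12 and 0.01.

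**5. Separation.** The documents give no covariate prevalences, so three sets were assumed. Simulation: n=417, covariates unrelated to outcome, separation tested by linear programming, 150–200 runs per cell. Entries are the share of runs separated at 5% / 10% failures.

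| Assumed prevalence | 37 parameters | 33 parameters | After p<0.25 screen | 37 parameters, n=334 |
|---|---|---|---|---|
| Several co-morbidities at 2–5% | 100% / 94% | 100% / 94% | 15% / 7% | 100% / 99% |
| Every level at least 10% | 80% / 17% | 71% / 12% | 7% / 2% | 94% / 33% |
| Nearly all levels 20% or more | 25% / 0% | 23% / 0% | 3% / 0% | 41% / 3% |

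The last column assumes that 20% of patients are lost to missing covariates (0.80×417 = 334). The screened model starts from about 7–9 parameters on average when the covariates are noise.

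Two further sets of maximum-likelihood fits gave failure in 99% / 89% and 99% / 83% of runs with several rare co-morbidities, and 69% / 7% and 84% / 15% with every level at least 10%. Over all checks without the screen, and at n=417, the ranges are 83–100% (rare co-morbidities), 69–84% at 5% and 7–17% at 10% failures (every level at least 10%), and 0–25% (nearly all levels 20% or more).

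**6. Odds ratios.** Median estimates over the scenarios; elimination by Wald p-values at 0.05.

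| Setting | 5% failures | 10% failures |
|---|---|---|
| True 2.0, full model | 2.4–2.7 | 2.0–2.5 |
| True 2.0, kept after elimination, no screen | 3.5–4.0 | 2.5–2.6 |
| True 2.0, kept after elimination, with screen | 3.5–4.0 | 2.5–2.7 |
| True 2.5, kept, maximum likelihood | 3.4–4.0 | 2.8 |
| True 2.5, kept, Firth | 3.3–3.8 | 2.7–2.8 |

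For the true 2.5, full-model medians over 5%, 10% and 15% failures were 2.8–3.2 by maximum likelihood and 2.2–2.6 by Firth, which always converged. Without the screen, the true 2.0 effect was kept in only 27–30% of runs at 5% failures and 49–58% at 10%.

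The screen therefore removes most separation, and Firth removes non-convergence and most full-model bias. Neither removes the inflation that comes from selection.

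**The case against.** **The screen may still apply.** The SAP keeps the protocol's order, univariate fits first, and it announces other departures (SVR12 window in 4.1.1, shift tables in 4.2.8.4, interim timing in 4.2.9). A reader might infer that the screen has certainly been abandoned. The documents do not settle that: the SAP is silent. Silence does not show that the screen survives either, because SAP 4.2.7.1 also replaces the protocol's Clopper-Pearson interval by Wilson's without comment. The ambiguity stands and matters, because separation with the screen is only 0–15%.

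**Thirty-seven is a ceiling.** True: race and IL28B are conditional and categories may be merged. But 33 parameters still leave 0.6–1.3 non-responders each. The 80% rule concerns missing data, and an unreported co-morbidity is coded as absent, so rare co-morbidities pass it. Merging cannot rescue a sparse yes/no covariate.

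**The model need not separate.** A reader might infer that the full model usually breaks down. That depends on prevalences and a failure rate that the documents do not give, and at 10% failures with every level at 10% or more it is uncommon. Maximum likelihood and Wald tests are likewise the default reading, not stated choices.

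**False predictors.** At least one noise covariate was kept in 57–75% of runs (64–67% in runs with no true predictor). It is tempting to blame sparsity, but 28 independent tests at 5% alone would give 1−0.95^28 = 76%. This is ordinary multiplicity.

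**The analysis is exploratory.** Both documents say so, and this limits the weight of the point. It does not make a divergent estimate reportable.

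**Conclusion.** The point holds in limited form. The SAP allows up to 37 candidate parameters (33 without race and IL28B) on about 21–42 expected non-responders, 0.6–1.3 per parameter and somewhat more if missing SVR12 adds failures. It omits the protocol's p<0.25 screen without declaring this, and has no rule for separation or sparse covariates.

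Under default maximum likelihood, separation of the full model ranges from near 0% to 100%. It is the rule if several co-morbidities have 2–5% prevalence, common at 5% failures if every level is at least 10%, and infrequent otherwise. Upward bias in odds ratios is clear at 5% failures and modest at 10%. All of this rests on assumed prevalences.

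A reader might go further and doubt the main result. Nothing here supports that: the primary SVR12 rate is a simple proportion and does not use these models. This is a correction worth making to the analyses for secondary objectives 2 and 4.

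**What to change.** In SAP 4.2.7.2.1:

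1. State that the protocol's univariate p<0.25 screen applies, or declare and justify dropping it.
2. Fit the univariate, multiple and adherence SVR12 models with Firth's penalised likelihood, with profile-likelihood tests and intervals. The univariate fits need it too, because a covariate with an empty cell diverges there as well.
3. Exclude sparse covariates by a numeric frequency threshold fixed without looking at SVR12.
4. Report bootstrap inclusion frequencies beside the final model, and state that its odds ratios remain inflated by selection, which Firth does not remove.

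Keeping only one of weight and BMI, and one of the ALT and AST ratios, is optional; no harm from either pair was shown.

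The cost is SAP wording, a model option available in SAS 9.4, and slightly more analysis work. Estimates will be less extreme. No new data are needed.

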#### 9.2.4 Investigator Selection Criteria

University centers and outpatient clinics qualified by training and experience in the management of patients with CHC will be selected to participate in this study. The AbbVie Affiliate Medical Director will ensure that sites participating in the study are representative of the medical practice in the country, have the ability to conduct the study and their availability of the target patient population. The type of the participating treating institute will be documented in the eCRF.

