## **9.9      Limitations of the Research Methods**

The limitations of observational studies, such as uncontrolled confounding by lack of randomization, and difficulties to clearly interpret treatment effects in the context of missing data are well known. Their validity can be increased by accurate outcome measurements, documentation of the most common confounders, sufficient length of follow-up and by activities to obtain complete recording of available data as well as by searches for missing key data.

The most important outcome measure in this study is HCV RNA. Missing or unrecorded follow-up HCV RNA data can in particular lead to an underestimation of the real SVR rate as compared to the SVR rate of interventional trials. Highly sensitive and quantitative diagnostic tests are required to measure HCV RNA levels in blood. In an observational study each center will be using its own test – either commercially available or so-called “home-brew” tests – which might change from one visit to the next within a patient data set. The challenge is to accurately and consistently document test properties such as the LLoD and the LLoQ to put the results into perspective of prior outcomes from randomized controlled trials with (usually) central laboratory assessments for all trial participants.

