4.2.4 Site and Researcher Information

Data of the study sites and of the Researcher will be presented in summary tables and listings.

The summary tables for site information will show absolute and relative frequencies for the institution type (private practice/ private hospital, general hospital, academic/ university hospital, other), the type of unit (general population, transplant, drug user, HIV/ HCV co-infection, hepatocellular carcinoma [HCC]), and the site location (urban, rural). Regarding type of unit multiple answers per site are possible.

The principle researcher experience will be summarized by presenting for each therapeutic specialty (hepatology, infectious disease, gastroenterology, internal medicine, transplant, general practitioner) the number and percentage of principle researchers, who have the specific experience. Furthermore, the number and percentage of sites with at least one researcher (i.e. including co-researcher) of the therapeutic specialty concerned and the number of HCV-infected patients typically seen per month at the site (<25, 25-50, 51-75, 76-100, >100), including the patients seen by co-researcher, will be summarized. Note: Multiple therapeutic specialties could be reported per researcher.

An overview of Tables for site and researcher information is given in Table 5.

Table 5 Overview of Outputs for Site and Researcher Information

Output Title	Output Short Name	Analysis Population
Site Information - <country>	tsi_<c>	Sites with patients
Researcher Experience- <country>	tre_<c>	Sites with patients

The layouts of the tables mentioned above are provided in Part II of the SAP (Table Shells).

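### Institute type is fixed within a site, but the SVR12 regressions test it as if patients were independent; its p-value is too small if sites differ for other reasons, by an amount the documents do not determine.

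*SAP*

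**What the plan says.** The SVR12 exploratory section of SAP 4.2.7.2.1 states: "Univariate and multiple logistic regression (MLR) methods will be used to investigate the impact of various explanatory covariates". The candidate list includes "Type of treating institute (Private Practice / Private Hospital, Academic / University Hospital, General Hospital, Other", with no reference category named. For elimination, "A p-value <0.05 will be used for the covariates to stay in the model in a backward elimination step". The adherence models later in the same section reuse these baseline variables and methods, with adherence forced in. Protocol 9.7.3.3 names the same covariate.

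Institute type describes the site. SAP 4.2.4 says: "The summary tables for site information will show absolute and relative frequencies for the institution type", and lists the same categories. Protocol 9.2.4 says: "The type of the participating treating institute will be documented in the eCRF".

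Neither document gives these models a site term, a random intercept, a GEE or a cluster-robust variance. On status, the SAP says: "These analyses will be of exploratory nature, data driven, and will be performed for CP population".

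**The concern.** An ordinary logistic model treats patients as independent given the covariates. For a covariate that is constant within a site, the null hypothesis it tests in effect is that institute type has no effect and that sites do not otherwise differ. Rejection can therefore come from a few unusual sites of any type. The information on this covariate depends heavily on the number of sites per type, not only on the number of patients.

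The documents give reasons why sites could differ. HCV RNA testing is left to the physician (Protocol 9.7.1, SAP 4.2.2). SVR12 still missing after imputation counts as failure (SAP 4.2.3), and the regressions use the core population, which keeps those patients. A site that seldom tests after treatment can thus show a lower SVR12 rate whatever its type. Protocol 9.9 adds: "In an observational study each center will be using its own test".

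At stake is secondary objective 2, predictive factors of response: academic versus general versus private care could be reported as a predictor of cure when the difference comes from a few sites.

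**Working it through.** **Planning figures.** The documents state no error rate for this test, so there is none to reproduce. The 417 evaluable patients come from SAP 3.2. Exact Clopper-Pearson widths are 6.00% (n=417, 90%), 5.99% (n=238, 95%) and 4.99% (n=334, 95%; the table prints 5.00%, and its limits match). Also 417/0.95 = 439, against 440 planned. These inputs are sound.

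**Assumed, because the documents are silent.** 10 to 40 sites; a between-site SD of 0 to 0.75 on the logit scale; three or four institute types.

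**What the SDs mean at SVR12 90%.** Site rate = expit(a + SD × z), with a set so that the average is 90%. The middle 80% of sites lie at expit(a ± 1.28 × SD). For SD 0.5, a = 2.295, giving expit(1.654) = 84% to expit(2.936) = 95%. The observed-scale ICC, Var(site rate)/(0.9 × 0.1), is 0.023.

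**Hand check by design effect.** Take four types (3 df, critical value 7.815) and 20 equal sites, so m = 417/20 = 20.85. The naive chi-square is inflated by about DE = 1 + (m − 1) × ICC, and the true rejection rate is P(χ²₃ > 7.815/DE).

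- ICC 0.02: DE = 1 + 19.85 × 0.02 = 1.397; 7.815/1.397 = 5.594; rate 13%.
- ICC 0.05: DE = 1 + 19.85 × 0.05 = 1.9925; 7.815/1.9925 = 3.922; rate 27%.

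Beta-binomial simulation of the same layout gave about 14-16% and 27-31% with the likelihood-ratio test.

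**Simulation with unequal sites.** 417 patients, no institute effect, institute type as the only covariate, SVR12 90%, nominal 5%. Ranges run over 10 to 40 sites and three or four types.

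| Site SD (logit) | Middle 80% of sites | Likelihood-ratio false-positive rate |
|---|---|---|
| 0 | all 90% | about 5-7% |
| 0.3 | 86-93% | 7-17% |
| 0.5 | 84-95% | 11-29% |
| 0.75 | 81-97% | 18-49% |

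Fewer sites give higher rates. At SD 0.5 with three types, one run gave 26%, 16% and 11% for 10, 20 and 40 sites.

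**Choice of test.** The SAP gives only a p-value threshold. A Wald test at SVR12 90% and SD 0.5 rejects about 9-23% of the time. At SVR12 95% only 417 × 0.05 = 21 failures are expected, and Wald becomes conservative. With four types it gives about 2-5% for 20 to 40 sites at SD 0.3 to 0.5; at SD 0.75 it gives 11.3% with 20 sites and 6.6% with 40. In these runs a type with no failures counted as non-significant.

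**Does a site-level test repair it?** Permuting institute type across whole sites (20 sites, three types) gave 4.3-6.3% where the ordinary likelihood-ratio test gave 12-31%. An overdispersion-scaled F-test with site-based degrees of freedom (four types, 15 to 40 sites, ICC 0.02-0.05) gave about 3-9% with equal sites and 5-14% with unequal sites, against 9-45% for the patient-level test. A random-intercept model was not simulated.

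**The case against.** The strongest reply is that nothing in the documents shows the site spread to be large. Assay differences are partly handled by a common 50 IU/mL rule with conditions on detection and quantification limits. A missing SVR12 value is filled first from flanking values and then from a later one, and only what is still missing becomes a failure. The full model also offers cirrhosis, genotype, prior treatment and other covariates that may absorb case-mix differences. The relevant quantity is the residual spread, for which there is no estimate, and the simulation leaves those covariates out. All of this stands, and it limits the size that can be claimed.

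The second reply is that the analysis is exploratory, that institute type is one of more than 20 candidates, and that "The categories pre-specified above could be modified in the analyses if this is supported by the data". This lowers the stakes. It excuses multiplicity and loose selection, but it does not make the patient the right unit for a site attribute.

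Two stronger readings are tempting. A reader might infer that institute type will be declared a predictor two to six times too often. That multiple needs a number of sites, a site spread and a choice of test that the documents do not give; across the assumptions tried, the excess runs from none to more than eightfold. A reader might also infer that false retention of institute type changes which other covariates survive elimination. That is possible, but it has not been computed.

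**Conclusion.** The point holds as a limited one. The cause and the direction can be read from the documents: a site-level covariate is tested at patient level, so its p-value is too small and its interval too narrow whenever residual SVR12 differences between sites exist. The size cannot be read from them. The simulated rates are conditional on 417 patients, 10 to 40 unequal sites, three or four types, institute type tested alone and the stated site SDs. With no site variation there is no material excess, and with a Wald test at SVR12 95% and modest spread there is little or none.

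The primary SVR12 estimate and the safety analyses do not depend on this test. The matter is worth correcting because institute type is a named candidate under secondary objective 2, enters the adherence models as well, and is easily over-interpreted.

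**What to change.** In SAP 4.2.7.2.1, for institute type only and in both the SVR12 and the adherence models:

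- Take it out of the p<0.05 backward selection. Report SVR12 by institute type descriptively, with the number of sites and of patients per type.
- If a p-value is wanted, obtain it by permuting institute type across whole sites. Where there are enough sites per type, a logistic model with a random site intercept and site-based degrees of freedom is an alternative. Name the test in the SAP.

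Patient-level covariates stay as planned.

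The cost is SAP wording and some programming, with no new data: SAP 6.1 already plans a data set of site information. The downside is a wider interval and less apparent significance for this one covariate. Any site-level test will be weak when sites per type are few, and approximate corrections can leave some excess when sites are few and unequal. In that case the descriptive table is the safer choice.
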